To ensure maintenance of the study blind in the ongoing ISIS 420915-CS2 study, TTR, RBP4, retinol, and NT-proBNP from the first 13 weeks of treatment in this study will not be available to the Sponsor, Investigators, Study Center Personnel, or the patients until the ISIS 420915-CS2 study is unblinded.

The mNIS+7 assessment will be conducted at Weeks 26, 52, 78, 104, 130, and 156. The NIS assessment will be conducted at Y4-W52 and Y5-W52. The Norfolk QOL-DN questionnaire is conducted at Weeks 26, 52, 78, 104, 130, 156, and Y4-W52 and Y5-W52. The Norfolk QOL-DN questionnaire should be the first assessment performed at these visits. If ISIS 420915 administration, ERG, or ophthalmology examinations are to be performed on the same day as an mNIS+7 or NIS assessment, they should be performed after the mNIS+7 or NIS assessment is complete. For Week 78 and Week 156 visits, 2 mNIS+7 assessments will be performed on separate days. A maximum of 2 weeks from the visit (Week 78 or Week 156) will be allowed to complete both assessments.

For Weeks 4-52 there is a \pm 7-day visit window. After Week 52 the visit window is \pm 10-day. All reasonable attempts should be made to ensure compliance with the visit schedule as outlined in the schedule of procedures (Appendix A). However, if a visit does not occur or is delayed, all subsequent visits should be calculated based on the time elapsed since Day 1 rather than from the date of the previous visit.

The Study Day 1 ECHO can be done any time in the screening period or up to 2 weeks after Day 1. The Day 1 ECHO is not done if the Week 65 ECHO was conducted in ISIS 420915-CS2. A \pm 2-week window is given for all other ECHOs.

During the treatment period, an ophthalmology examination will be performed at Weeks 26, 52, 78, 104, 130, 156, and 2 times in each subsequent year (26^{th} and 52^{nd} week of each year). An ERG examination will be performed at Weeks 78 and 156. A window of \pm 2 weeks is allowed for these eye examinations. Early termination ERG and ophthalmology examinations are only done if the patient discontinues treatment after \geq 9 months of dosing or unless deemed necessary by Investigator or Study Medical Monitor.

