3.2.1.2 Scoring of Assessment Instruments

mNIS+7

The mNIS+7 consists of two composite scores: the NIS composite score (maximum of 244 points) and the modified +7 composite score (maximum of 102.32 points).

NIS

The NIS composite score consists of 4 components:

- Cranial Nerves (NIS-C), maximum 40 points
- Muscle Weakness (NIS-W), maximum 152 points
- Reflexes (NIS-R), maximum 20 points
- Sensation (NIS-S), maximum 32 points.

Questions that make up each composite are listed in the table below.

NIS composite	Question number
Cranial Nerves	1-5
Muscle Weakness	6-24
Reflexes	25-29
Sensation	30-37

Note that each question is separately assessed for the right and left side of the body, meaning that questionnaire is comprised of 74 subcomponents (37 for the left side, and 37 for the right side).

Modified +7

The modified +7 composite score consists of 4 components:

- 1 component for autonomic nerve assessment:
 - Heart Rate to Deep Breathing (HRDB), minimum -3.72 points, maximum 3.72 points,
- 1 component for the nerve conduction assessment of the lower and upper limbs:
 - \circ Nerve Conduction Tests (Σ 5 NC), maximum 18.6 points from 5 subcomponents (PMAK, TMAK, UMAE, USAW, SSAB) with minimum -3.72 points and maximum +3.72 points each,
- 2 components for the sensory nerve assessment:
 - o Touch-Pressure (TP), maximum 40 points
 - Heat-Pain (HP), maximum 40 points.
 NOTE: Testing for both TP and HP is done at up to 10 sites on one side of the body. To obtain the full body score for TP and HP, the summation scores from all 10 anatomical sites

is multiplied by 2 (only one side of the body is tested as FAP is symmetrical neuropathy, identical results are assumed for the other side).

Component	Data entry convention /Comment	Pre-processingstep
Heart Rate Deep Breathing	If HRDB could not be measured due to pacemaker or arrhythmia, MC Core checked either the box "no reliable data to due pacemaker" or "no reliable measure points due to arrhythmia," and left the HRDB score as blank in the BioClinica database	None
	If HRDB was not measured in error or missing for other reasons, MC Core entered a "-9" into the BioClinica database	Set "-9" to missing
	Transform normaldeviate score so that larger values coincide with worse outcomes	Multiply subcomponent score by "-1"
Nerve conduction test	If the nerve attribute was not tested in error, MCCore entered a "-9" into the BioClinica database	Set "-9" to missing

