	For all 5 subcomponent (SSAB, USAW, UMAE, PMAK, TMAK) transform subcomponent normal deviate score so that larger values coincide with worse outcomes	Multiply each subcomponent score by "-1"
Touch Pressure	If an anatomical site was assessed, , MC Core entered a "O", "1" or "2" into the BioClinica database	None
	If an anatomicalsite was skipped because it was assumed to be< 95%, MC Core left the field blank in the BioClinica database (the last assessed more distalanatomical site has a "O" entered)	Set blank field to "O"
	If an anatomicalsite was not tested in error, MC Core entered a "-9" into the BioClinica database	Set "-9" to missing
Heat Pain	If an anatomicalsite was assessed, MC Core entered a "O", "1" or "2" into the BioClinica database	None
	If an anatomical site was skipped because it was assumed to be< 95%, MC Core left the field blank in the BioClinica database (the last assessed more distalanatomical site has a "O" entered)	Set blank field to "O"

If an anatomical site was not tested in error, MC Core entered a "-9" into the BioClinica database	Set "-9" to missing
--	---------------------

Additionally, for Heat Pain and Touch Pressure, the composite scores are calculated by multiplying the sum of the 10 averaged subcomponent scores (defined below) by 2.

NIS+7

The NIS+7 consists of two composite scores: the NIS composite score (above) and the +7 composite score (maximum of 26.04 points).

+7

The +7 composite score consists of 3 components:

- 1 component for autonomic nerve assessment:
 - Heart Rate to Deep Breathing (same as modified +7), minimum -3.72 points, maximum 3.72 points,
- 1 component for the peripheral nerve assessment of the lower limb:
 - Nerve Conduction Tests (LS NC nds), maximum 18.6 points from 5 subcomponents (PMAK, PMCVK, PMLA, TMLA, SSAB) with minimum -3.72 points and maximum +3.72 points each. Please note that 3 of the subcomponents used in +7 (PMCVK, PMLA, TMLA) are different from 3 of the subcomponents used in modified +7 (TMAK, UMAE, USAW).
- 1 component for the sensory nerve assessment
 - o Vibration Detection Threshold (VDT), minimum -3.72 points, maximum 3.72 points.

Due to the testing algorithm and the MC Core data entry conventions, raw+ 7 data need to undergo a pre-processing step before the scores can be derived. The different pre-processing steps are summarized in the table below.

Component Data entry convention /Comment		Pre-processing step

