For both CS2 and CS3, two independent assessments of mNIS+7 are planned at early termination visits. If both assessments are within the same visit window, the mean of the two will be used. At early terminations, in the event that only one subcomponent has been performed, the single subcomponent will be used in place of the mean value for that visit for the averaged subcomponent score.

Imputation of missing averaged subcomponents

If a patient has completed at least part of the mNIS+7/NIS+7 at a visit then the following imputation method will be used to impute this missing assessment level data for the purposes of determining component scores for summary and analysis.

The following missing data imputation steps will be considered and will be used as described below for Groups A, B, and C:

- Step 1: If at least 50% of averaged subcomponent scores within a component are available, the
 missing averaged subcomponent scores will be set to equal to the mean of the patient's other
 non-missing averaged subcomponent scores in that component. The component score is then
 calculated.
- Step 2 (Parent study baseline): In the unlikely event that there are more than 50% of the averaged subcomponents scores within a component that are missing at baseline, the missing averaged subcomponent scores will be set to equal to mean baseline averaged subcomponent score from the parent study Randomized Set (across treatment groups). The component score is then calculated. This is the same definition as used in the parent study.
- Step 3 (OLE study baseline and CS2 and CS3 post-baseline visits): For certain components, and
 only under certain conditions which will be listed below, the missing averaged subcomponent
 scores at that visit within that component only will be set equal to the mean averaged
 subcomponent score among the subjects randomized to placebo in the parent study in the
 Randomized and Enrolled set for CS2 and CS3 respectively. The component score is then
 calculated. This is the same definition as used in the parent study for post-baseline visits.

If a post-baseline assessment does not fall into the scheduled analysis windows, there is no obvious visit on which the mean subcomponent scores in the placebo group can be derived. In order to apply step 3, the following visits will be used to derive the mean scores in the placebo group:

Timing of Assessment	Visit used for deriving the mean subcomponent scores in	
	the placebo group*	

Before Week 26	OLE baseline

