if the recorded response was classified "not evaluable." After this, imputation step 1 and 2 will be applied.

If, after applying step 1 for post-baseline visits, 4 out of the 5 components of the NIS+7 composite score (NIS-C, NIS-R, NIS-S, NIS-W, or NCT) are available and only one is missing at that visit, then step 3 will be applied for that the missing component.

Mean averaged subcomponent score used in the imputation described in step 3 are derived from the averaged subcomponent scores before step 1 imputation among the group of patients who were randomized to placebo in the parent study.

Note that these components are *not* used in the nerve conduction component of the *modified* +7, therefore Group B only includes the NCT component of the NIS+7 and not the NCT component of the mNIS+7.

- Group C: The two components, HRDB and vibration tests, have only one subcomponent. Missing data for these averaged subcomponents score will be imputed as follows:
 - For Parent study baseline, the missing averaged subcomponent scores will be set to equal
 to the mean baseline averaged subcomponent score from the parent study Randomized Set
 (across treatment groups). This is the same definition as used in the parent study.
 - o For OLE study baseline and CS2 and CS3 post-baseline visits, the missing averaged subcomponent scores at that visit will be set equal to the mean averaged subcomponent score among the subjects randomized to placebo in the parent study in the Randomized and Enrolled set for CS2 and CS3 respectively. If a post-baseline assessment does not fall into the scheduled analysis windows, there is no obvious visit on which the mean subcomponent scores in the placebo group can be derived. In order to derive the mean scores in the placebo group, the following visits will be used:

Timing of Assessment	Visit used for deriving the mean subcomponent scores in the placebo group*
Before Week 26	OLE baseline
Between Week 26 and Week 52	Week 26
Between Week 52 and Week 78	Week 52
Between Week 78 and Week 104	Week 78
Between Week 104 and Week 130	Week 104
Between Week 130 and Week 156	Week 130
After Week 156	Week 156

^{*}Note: the Placebo group refers to the group of patients randomized to placebo in the parent study in the Enrolled set for CS3.

Composite Score

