9.2.2.3 Itegrated Summary of Efficacy based on CS2 and CS3 data

Descriptive summary statistics:

Descriptive summary statistics for absolute values, change or percent change from ISIS 420915 baseline, if applicable, will be provided by analysis visits for below endpoints based on 420915 FAS, unless specify.

- mNIS+7 Composite Score (On-Treatment)
- mNIS+7 Composite Score (On-Treatment) by IM
- Modified +7 and +7 Composite Scores (On-Treatment)
- NIS+7 Composite Scores (On-Treatment)
- NIS Composite and Component Scores (On-Treatment)
- Modified +7 Component Scores (On-Treatment)
- +7 Component Scores (On-Treatment)
- Norfolk QOL-DN Total Score (On-Treatment)
- Norfolk QOL-DN Total Score (On-Treatment) by IM
- Norfolk QOL-DN Symptoms Domain Score (On-Treatment) Stage 1 Patients
- Norfolk QOL-DN Physical Functioning/Large Fiber Neuropathy Domain Score (On-Treatment)
 Stage 2 Patients
- Norfolk QOL-DN Domain Scores (On-Treatment)
- NSC Total Score and Domain Scores (On-Treatment)
- Modified Body Mass Index and Body Mass Index (On-Treatment)
- Transthyretin (TTR) and Retinol Binding Protein 4 (RBP4) (On-Treatment)
- Transthyretin (TTR) (On-Treatment) by IM
- SF-36 Component Summary Scores and Domain Scores (On-Treatment)
- NT-proBNP Result (pmol/L) and Log-Transformed NT-proBNP Result (On-Treatment), outputs will be repeated based on ISIS 420915 CM-ECHO set
- mNIS+7, NIS+7, NIS, Modified +7, +7 Composite and Component Scores (Post-Treatment)
- Norfolk QOL-DN Total and Domain Scores (Post-Treatment)
- SF-36 Scores (Post-Treatment)
- NSC Score (Post-Treatment)
- Global Longitudinal Strain (%) (On-Treatment) based on ISIS 420915 Enrolled Patients, ISIS 420915 ECHO Subgroup, and ISIS 420915 CM-ECHO Set
- Assessment of Global Left Ventricular Size and Function LV Mass (g) (On-Treatment) based on ISIS 420915 Enrolled Patients, ISIS 420915 ECHO Subgroup, and ISIS 420915 CM-ECHO Set
- mNIS+7 Composite Score: Response Rate by Threshold Value by Visit (On-Treatment) based on ISIS 420915 FAS

- Summary of PND Score Shift from Baseline by Visit (On-Treatment) based on ISIS 420915
 FAS
- Summary of PND Score Change from Baseline by Visit (On-Treatment) based on ISIS 420915
 FAS
- Summary of Select Questions from NSC (On-Treatment) and (Post-Treament) based on ISIS 420915 FAS

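### The NIS+7 imputation rule gives a non-missing +7 and NIS+7 when a complete NIS was done but none of the three +7 tests was observed

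*Combined protocol and SAP*

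**What the plan says.** SAP 3.2.1.2 defines the scores. For the NIS, "The NIS composite score consists of 4 components": NIS-C, NIS-W, NIS-R and NIS-S. For the +7, "The +7 composite score consists of 3 components": HRDB, NCT and VDT. NIS+7 is the sum of the two, so it has seven components.

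SAP 3.2.1.3 sets the imputation rules.

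- Entry: "If a patient has completed at least part of the mNIS+7/NIS+7 at a visit then the following imputation method will be used". Everything is missing only if the visit was missed or out of window, or the whole assessment was not conducted.
- Step 3 for NIS+7, after baseline: if "4 out of the 5 components of the NIS+7 composite score (NIS-C, NIS-R, NIS-S, NIS-W, or NCT) are available" and only one is missing, the missing one is set to the mean among patients randomized to placebo in the parent study.
- Group C: "The two components, HRDB and vibration tests, have only one subcomponent". After the parent-study baseline, each is replaced by the placebo-group mean whenever it is missing. No minimum number of other tests is required.
- Composites are sums of the imputed components. They are missing only if a component is still missing after imputation.

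The parallel step 3 rule for mNIS+7 requires six of seven counted components, leaving out only HRDB.

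On schedule, Protocol 6.1.2 states: "The NIS assessment will be conducted at Y4-W52 and Y5-W52". Appendix A also replaces mNIS+7 with NIS at early termination from Years 4-5.

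**The concern.** The step 3 condition is meant to allow a group mean only when one component is missing and the rest of the examination was observed. For NIS+7 it does not do that, because two of the three +7 tests are outside the count and are filled separately without limit. The four NIS components alone satisfy it, and nothing else in the section requires any +7 test to have been done.

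This matters because the final analysis uses these scores. SAP 9.2.1 adds a statistical analysis of change from the parent-study baseline for NIS+7 and +7, and post-treatment descriptive tables. SAP 9.2.2.3 adds combined CS2 and CS3 summaries of the +7 and NIS+7 composites and the +7 components. A patient with no +7 test at a visit would be counted there as having been measured.

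**Working it through.** **Inputs.** Component maxima come from SAP 3.2.1.2 and Appendix 1, Tables 1 to 3; rules come from SAP 3.2.1.3.

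**The plan's own totals reproduce.**
- NIS: 40 + 152 + 20 + 32 = 244.
- +7: 3.72 (HRDB) + 18.6 (NCT) + 3.72 (VDT) = 26.04.
- NIS+7: 244 + 26.04 = 270.04, from 4 + 3 = 7 components.
- The stated five in the step 3 rule is 7 minus the two Group C components.

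**Post-baseline examination with all four NIS components and no +7 test.**

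| | NIS+7 rule | mNIS+7 rule |
|---|---|---|
| Components in the score | 7 | 8 |
| Counted by step 3 | 5 | 7 |
| Counted and available | 4 | 4 |
| Required | 4 | 6 |
| Step 3 applies | yes, fills NCT | no |
| Group C fills | HRDB, VDT | HRDB |
| Result | +7 and NIS+7 non-missing | modified +7 and mNIS+7 missing |

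The +7 is then 26.04/26.04 = 100% imputed. In NIS+7 the imputed part is 26.04/270.04 = 9.6% of the maximum.

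**How many patterns are affected.** Each component is either available or missing.
- NIS+7: 2^7 = 128 patterns. A complete score needs at most one of the five counted components missing (1 + 5 = 6 ways) with any state of HRDB and VDT (4 ways): 6 x 4 = 24 patterns. Exactly one of these has no +7 test observed.
- mNIS+7: 2^8 = 256 patterns, of which (1 + 7) x 2 = 16 give a complete score. None has all modified +7 tests missing, because NCT, touch-pressure and heat-pain are three counted components.

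**What enters the tables.** Let f be the share of reported +7 values at a visit that are fully imputed. The documents do not give f; 2%, 5% and 10% are assumptions.
- n: of every 100 reported values, 98, 95 or 90 would rest on any +7 test.
- Absolute +7: every affected patient has the same constant at that visit. If the observed values have SD s and the filler lies d from their mean, the variance is (1-f)s² + f(1-f)d². With d = 0 the SD ratio is sqrt(1-f) = 0.990, 0.975 and 0.949. The filler is the placebo-group mean, so d need not be 0 for patients randomized to active drug (90 of the 135 planned, SAP 1.1).
- Change in +7: an affected patient contributes a constant minus the patient's own baseline, with variance s². Assuming equal variances at both times, correlation r and equal mean change, observed change has variance 2s²(1-r). The SD ratio is sqrt{[(1-f)·2(1-r) + f] / [2(1-r)]}.

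| r (assumed) | f = 5% | f = 10% |
|---|---|---|
| 0.3 | sqrt(1.38/1.40) = 0.993 | sqrt(1.36/1.40) = 0.986 |
| 0.7 | sqrt(0.62/0.60) = 1.017 | sqrt(0.64/0.60) = 1.033 |
| 0.9 | sqrt(0.24/0.20) = 1.095 | sqrt(0.28/0.20) = 1.183 |

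The SD of change falls for r below 0.5 and rises above it.

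**The case against.** **The count is a convention, inherited from the parent study.** Single-item tests go to Group C by design, the mNIS+7 rule also leaves out HRDB, and the SAP says step 3 matches the parent-study definition. That explains the wording. But the convention is harmless in mNIS+7, where one small component is uncounted, and fails in +7, where two of three are. Consistency with the parent study does not turn three imputed tests into an observation.

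**The full battery is scheduled at Weeks 26 to 156.** True. The documents give no sign of how often a NIS is completed without any +7 test there, so no frequency can be claimed.

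**Years 4-5.** A reader might infer that, because only the NIS is scheduled, every +7 value at Y4-W52 and Y5-W52 would be imputed, with SD zero in the tables. The documents do not support that. SAP 3.4.1 names only the NIS, among these scores, for Year 4-5 by-visit summaries, and the mNIS+7 window table in Appendix 3 stops at Week 156 while the NIS table continues. What remains is that no text says +7 and NIS+7 are not derived there, so derived data and listings are exposed. Post-treatment tables are possibly exposed too, but only for a termination examination more than 52 days after the last dose. That visit is ideally within 14 days, and the post-treatment windows list only NT-proBNP, BMI/mBMI and the PD panel.

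**Importance.** NIS+7 and +7 are not among the protocol's efficacy endpoints or those listed in SAP 3.4.2, and the study has no formal hypotheses. This stands and keeps the severity low.

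**Conclusion.** The rule is wrong as written; severity is minor. A post-baseline examination with all four NIS components available and no +7 test receives a +7 that is 100% placebo-group means and a NIS+7 treated as observed. The mNIS+7 rule correctly leaves its own scores missing for the same examination.

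Three stronger readings should be avoided.
- Not every NIS-only examination qualifies: if one NIS component is still missing after step 1, only three of the five counted components are available and step 3 does not apply.
- The defect does not generally shrink the SD. The sqrt(1-f) figures hold only for absolute +7 with the filler at the observed mean; for change the direction depends on r.
- mNIS+7, the lead efficacy score, is not affected.

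The certain consequences are an overstated n, a constant absolute +7 for affected patients at a visit, and a change that contains no +7 measurement from that visit. Their size depends on a frequency the plan does not give. The conclusion rests on a literal reading of SAP 3.2.1.3 for post-baseline visits. Whether the five-component condition covers the OLE baseline is unclear, since step 3 names that baseline but the condition refers to post-baseline visits.

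**What to change.** In SAP 3.2.1.3, add one condition: when none of NCT, HRDB and VDT was observed at a visit, do not apply step 3 to NCT or Group C to HRDB and VDT for this purpose, and set +7 and NIS+7 to missing. State that +7 and NIS+7 are not derived at NIS-only visits (Y4-W52, Y5-W52 and early termination from Years 4-5). Apply the same condition to the CS2 visits shown in the CS3 tables, so that both periods are derived alike.

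This removes one of the 24 patterns that now give a complete NIS+7, leaving 23. A tighter threshold is not needed to correct the error and is open to debate. Requiring two of the three tests would keep a +7 with NCT imputed, which is 18.6/26.04 = 71% of the maximum, and drop one in which only NCT was observed. Counting all seven components and requiring six would cut the complete patterns to 8 of 128.

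The cost is a sentence in the SAP, one line in the derivation, probably a few fewer +7 and NIS+7 values, and a small departure from the parent-study derivation that should be noted in the report.
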